2.3. Other Secondary Endpoints

- Proportion of patients with EASI-75, EASI-90 and EASI-50 by visit
- Proportion of patients with IGA Score of 0 or 1 and a reduction ≥ 2 points from Baseline by visit
- Percentage change from Baseline in EASI Score by visit
- Percentage change from Baseline in Pruritus NRS by visit
- Percentage of patients with Pruritus NRS change of ≥ 4 from Baseline by visit
- Percentage of patients with a Pruritus NRS score of ≥ 4 points at Baseline who achieve a ≥ 4 -point reduction from Baseline by visit
- Change from Baseline in Sleep-Loss score by visit
- Change from Baseline in DLQI/CDLQI by visit
- Change from Baseline in EQ5D by visit

- Change from Baseline in POEM by visit
- Change from Baseline in PROMIS Anxiety measure by visit
- Change from Baseline in PROMIS Depression measure by visit
- Change in ACQ-5 score from Baseline to Week 16 in patients who have self-reported comorbid asthma
- Percentage change from Baseline to Week 16 in SCORAD

3. STUDY DESIGN

This is a randomized, double-blind, placebo-controlled, parallel-group study which is 52 weeks in duration. The study is designed to confirm the safety and efficacy of lebrikizumab as monotherapy for moderate-to-severe atopic dermatitis utilizing a 16-week induction treatment period and a 36-week maintenance treatment period (Figure 1).

Eligible adult and adolescent (≥ 12 to < 18 years weighing ≥ 40 kg) patients with moderate-to-severe AD for at least one year, defined according to the American Academy of Dermatology Consensus Criteria, an EASI Score of ≥ 16 , an IGA score of ≥ 3 and a BSA of $\geq 10\%$ will be enrolled.

During the 16-week Induction Period, approximately 400 patients will be stratified and randomized 2:1 to either 250 mg lebrikizumab (loading dose of 500 mg given at Baseline and Week 2) or placebo by SC injection Q2W. All study drug injections will be administered in the clinic.

After completion of the Week 16 visit, patients who have responded to treatment [defined as having an IGA of 0 or 1 or a 75% reduction in EASI from Baseline to Week 16 (EASI-75)] will enter the Maintenance Period and will be re-randomized 2:2:1 to one of the following treatment groups: lebrikizumab 250 mg Q2W, lebrikizumab 250 mg Q4W, or placebo Q2W. Patients will be instructed to self-administer study drug at home.

Patients who do not achieve an IGA of 0 or 1 or an EASI-75 at Week 16 and those patients not maintaining an EASI-50 response following re-randomization at Week 24, 32, 40 or 48 will be assigned to an Escape Arm and receive lebrikizumab 250 mg as open-label treatment Q2W through Week 52. Patients not achieving an EASI-50 response after 8 weeks of treatment in the Escape Arm will be terminated from the study.

Efficacy will be measured through the IGA, EASI, BSA, SCORAD, Pruritus and Sleep-loss scores.

Safety will be assessed by monitoring adverse events, serum chemistry, hematology and urinalysis laboratory testing, physical examination, pulse and blood pressure. An independent Data Safety Monitoring Board will monitor patient safety by conducting formal reviews of accumulated safety data periodically throughout the trial. Additionally, adolescents will be monitored for hormones.

Quality of life and impact of disease will be assessed using the POEM, DLQI/CDLQI, EQ-5D and PROMIS Anxiety and Depression measures. Patients reporting comorbid asthma at study entry will complete the ACQ-5.

Serum samples will be collected for pharmacokinetic analysis and immunogenicity.

Photographs of a selected target lesion will be obtained in a subset of patients participating in this study.

Patients completing this 52-week study will be offered the option of continued treatment in a separate long-term extension study (DRM06-AD07).

[figure not shown]
Patients who early terminate or choose not to enter the long-term extension study will undergo a follow-up visit approximately 12 weeks after the last study drug injection for safety follow-up.

A patient is considered to have completed the study if he/she has completed the last scheduled visit:

- For subjects continuing into LTE, upon completion of week 52 visit and rolling into LTE study
- For subjects not continuing into LTE, when subject had either week 52 or ETV, and safety follow up visit (12 weeks after last IP administration)

The end of the study is defined as the date of the last visit of the last patient in the study shown in the Schedule of Visits and Procedures.

Figure 1: Study Schema

* Responder is defined as having an IGA of 0 or 1 or a 75% reduction in EASI from Baseline to Week 16 (EASI-75)

3.1. Duration of the Study

The total duration of a patient's participation in this study will be approximately 66 weeks (Screening: maximum duration of 30 days; Induction Period: 16 weeks; Maintenance Period: 36 weeks; Follow Up: 12 weeks from last dose at Week 50).

3.2. Study Population and Number of Patients

Approximately 400 patients with moderate to severe atopic dermatitis, including approximately 50 adolescent patients (≥ 12 to < 18 years, weighing ≥ 40 kg).

4. SELECTION OF PATIENTS

Prospective approval of protocol deviations to recruitment and enrollment criteria, also known as protocol waivers or exemptions, is not permitted.

4.1. Inclusion Criteria

Patients must meet all the following criteria to be eligible for this study:

1. Adults and adolescents (≥ 12 to < 18 years of age and weighing ≥ 40 kg).
2. Chronic AD (according to American Academy of Dermatology Consensus Criteria) that has been present for ≥ 1 year before the screening visit.
3. Eczema Area and Severity Index (EASI) score ≥ 16 at the baseline visit.
4. Investigator Global Assessment (IGA) score ≥ 3 (scale of 0 to 4) at the baseline visit (see Section 8.2.1).
5. $\geq 10\%$ body surface area (BSA) of AD involvement at the baseline visit.
6. History of inadequate response to treatment with topical medications; or determination that topical treatments are otherwise medically inadvisable.
7. Apply a stable dose of non-medicated topical moisturizer at least twice daily for ≥ 7 days prior to the baseline visit.
8. Completed electronic diary entries for pruritus and sleep-loss for a minimum of 4 of 7 days preceding randomization.
9. Willing and able to comply with all clinic visits and study-related procedures and questionnaires.
10. For women of childbearing potential: agree to remain abstinent (refrain from heterosexual intercourse) or use a highly effective contraceptive method during the treatment period and for at least 18 weeks after the last dose of lebrikizumab or placebo.

NOTE: A woman of childbearing potential (WOCBP) is defined as a postmenarcheal female, who has not reached a postmenopausal state (≥ 12 continuous months of amenorrhea with no identified cause other than menopause) and has not undergone surgical sterilization (removal of ovaries and/or uterus).

NOTE: The following are highly effective contraceptive methods: combined (estrogen and progestogen containing) hormonal contraception (oral, intravaginal, transdermal) associated with inhibition of ovulation, progestogen-only hormonal contraception (oral, injectable, implantable) associated with inhibition of ovulation, intrauterine device (IUD), intrauterine hormone-releasing system (IUS), bilateral tubal occlusion, vasectomized partner, or sexual abstinence. The reliability of sexual abstinence should be evaluated in relation to the duration of the clinical trial and the preferred and usual lifestyle of the patient. Periodic abstinence (e.g., calendar, ovulation, symptothermal, or postovulation methods) and withdrawal are not acceptable methods of contraception.

11. Male patients must agree to use an effective barrier method of contraception during the study and for a minimum of 18 weeks following the last dose of study drug if sexually active with a female of child bearing potential
12. Provide signed informed consent/assent as described in Section [10.2](#).

4.2. Exclusion Criteria

Patients meeting any of the criteria below will be excluded from this study:

1. Participation in a prior lebrikizumab clinical study.
2. History of anaphylaxis as defined by the Sampson criteria ([Sampson, 2006](#)).
3. Treatment with topical corticosteroids, calcineurin inhibitors or phosphodiesterase-4 inhibitors such as crisaborole within 1 week prior to the baseline visit.
4. Prior treatment with dupilumab or tralokinumab.
5. Treatment with any of the following agents within 4 weeks prior to the baseline visit:
 - a. Immunosuppressive/immunomodulating drugs (e.g., systemic corticosteroids, cyclosporine, mycophenolate-mofetil, IFN- γ , Janus kinase inhibitors, azathioprine, methotrexate, etc.)
 - b. Phototherapy and photochemotherapy (PUVA) for AD.
6. Treatment with the following prior to the baseline visit:
 - a. An investigational drug within 8 weeks or within 5 half-lives (if known), whichever is longer.
 - b. B Cell-depleting biologics, including rituximab, within 6 months.
 - c. Other biologics within 5 half-lives (if known) or 16 weeks, whichever is longer.
7. Use of prescription moisturizers within 7 days of the baseline visit.
8. Regular use (more than 2 visits per week) of a tanning booth/parlor within 4 weeks of the screening visit.
9. Treatment with a live (attenuated) vaccine within 12 weeks of the baseline visit or planned during the study.
10. Uncontrolled chronic disease that might require bursts of oral corticosteroids, e.g., co-morbid severe uncontrolled asthma (defined by an ACQ-5 score ≥ 1.5 or a history of ≥ 2 asthma exacerbations within the last 12 months requiring systemic [oral and/or parenteral] corticosteroid treatment or hospitalization for > 24 hours).
11. Active chronic or acute infection requiring treatment with systemic antibiotics, antivirals, antiparasitics, antiprotozoals, or antifungals within 2 weeks before the baseline visit, or superficial skin infections within 1 week before the baseline visit.
NOTE: patients may be rescreened after infection resolves.
12. Evidence of active acute or chronic hepatitis (as defined by the Department of Health & Human Services Centers for Disease Control and Prevention) or known liver cirrhosis.
13. Diagnosed active endoparasitic infections or at high risk of these infections.

14. Known or suspected history of immunosuppression, including history of invasive opportunistic infections (e.g., tuberculosis [TB], histoplasmosis, listeriosis, coccidioidomycosis, pneumocystosis, and aspergillosis) despite infection resolution: or unusually frequent, recurrent, or prolonged infections, per the Investigator's judgment.
15. History of human immunodeficiency virus (HIV) infection or positive HIV serology at screening.
16. In the Investigator's opinion, any clinically significant laboratory results from the chemistry, hematology or urinalysis tests obtained at the screening visit.
17. Presence of skin comorbidities that may interfere with study assessments.
18. History of malignancy, including mycosis fungoides, within 5 years before the screening visit, except completely treated in situ carcinoma of the cervix, completely treated and resolved non-metastatic squamous or basal cell carcinoma of the skin.
19. Severe concomitant illness(es) that in the Investigator's judgment would adversely affect the patient's participation in the study. Any other medical or psychological condition that in the opinion of the Investigator may suggest a new and/or insufficiently understood disease, may present an unreasonable risk to the study patient because of his/her participation in this clinical trial, may make patient's participation unreliable, or may interfere with study assessments.
20. Pregnant or breastfeeding women, or women planning to become pregnant or breastfeed during the study.

5. STUDY DRUG

5.1. Investigational Medicinal Product

Lebrikizumab is a sterile liquid solution containing 125 mg/mL lebrikizumab, histidine acetate, sucrose, polysorbate 20, and sterile water for injection, USP, pH 5.4–6.0. Placebo solution is identical in appearance and content to the active solution except for lebrikizumab. All study drug (lebrikizumab and placebo) will be supplied as a sterile pre-filled syringe with a pre-assembled needle safety device (PFS-NSD). Each pre-filled syringe is intended for a single 2 mL dose (250 mg) administered subcutaneously (SC).

5.2. Storage and Labeling

Study drug is to be stored under refrigerated conditions (2–8°C) and protected from excessive light and heat. Study drug should not be frozen, shaken or stored at room temperature. Temperature excursions outside of 2–8°C must be reported to the Sponsor or the designee. Clinical trial material will be labeled according to country's regulatory requirements.

5.3. Patient Randomization

Patients will be assigned a unique identifier by the sponsor. Any patient records, datasets or tissue samples that are transferred to the sponsor will contain the identifier only; patient names or any information which would make the patient identifiable will not be transferred. All patients

will be randomly allocated to receive the study treatment using an electronic data capture system at the Baseline visit. The allocation to treatment will be prospectively stratified by geographic region (US versus EU versus rest of world), age (adolescent patients 12 to <18 years versus adults ≥18 years) and disease severity (IGA 3 versus 4). At the Baseline visit (Day 1), once a patient is considered eligible to participate in the study, demographic and stratification information will be entered into the EDC system to receive a medication number assigning a kit to a patient.

During the Maintenance Period, the EDC will be used to re-randomize a patient to a maintenance treatment based on the IGA or EASI score at Week 16.

5.3.1. Induction Period (Day 1 to Week 16)

Patients will be randomized 2:1 to one of the following treatment groups:

- Lebrikizumab 250 mg Q2W: 500 mg lebrikizumab administered at Baseline and Week 2 (loading dose; two PFS-NSD) and 250 mg Q2W through Week 14
- Placebo: 4 mL (two PFS-NSD) administered at Baseline and Week 2 and 2 mL Q2W through Week 14

5.3.2. Maintenance Period (Week 16 to Week 52)

After completion of the Week 16 visit, patients who have responded to treatment [defined as having an IGA score of 0 or 1 or, at least a 75% reduction in EASI from Baseline to Week 16 (EASI-75)] will be re-randomized 2:2:1 to one of the following treatment groups:

- Lebrikizumab 250 mg Q2W: 250 mg lebrikizumab given every 2 weeks through Week 50
- Lebrikizumab 250 mg Q4W: 250 mg lebrikizumab given every 4 weeks through Week 50
- Placebo: placebo given every 2 weeks

Responders who received placebo during the first 16 weeks of the study and who are re-randomized to lebrikizumab arms will receive a loading dose of lebrikizumab of either 500 mg given at Week 16 or 500 mg given at Weeks 16 and 18, based on the active treatment group assigned in Maintenance. To maintain study blinding, all patients re-randomized in the Maintenance period will receive the same number of injections at all visits throughout the Maintenance Period using an appropriate combination of active and placebo injections ([Table 2](#)).

Table 2: Maintenance Period Dosing Schedule by Treatment Group

Induction Treatment Assignment	Maintenance Treatment Assignment	Maintenance Loading Dose	Week 20, 24, 28, 32, 36, 40, 44, 48	Week 22, 26, 30, 34, 38, 42, 46, 50
Active	Lebrikizumab 250 mg Q2W	Week 16: one active and one placebo injection Week 18: one active and one placebo injection	One active injection	One active injection
	Lebrikizumab 250 mg Q4W	Week 16: one active and one placebo injection Week 18: two placebo injections	One active injection	One placebo injection
	Placebo	Week 16: two placebo injections Week 18: two placebo injections	One placebo injection	One placebo injection
Placebo	Lebrikizumab 250 mg Q2W	Week 16: two active injections Week 18: two active injections	One active injection	One active injection
	Lebrikizumab 250 mg Q4W	Week 16: two active injections Week 18 two placebo injections	One active injection	One placebo injection
	Placebo	Week 16: two placebo injections Week 18: two placebo injections	One placebo injection	One placebo injection

5.3.3. Escape Arm

Patients who require topical or systemic rescue treatment (Section 6.3) for atopic dermatitis during the Induction Period, or, are non-responders at Week 16, will be eligible for treatment in an Escape Arm where patients will receive lebrikizumab Q2W from Week 16 through Week 52. In addition, patients who do not maintain an acceptable response during the Maintenance Period (have an EASI score <50% of baseline), will be eligible for the Escape Arm.

To enter the Escape Arm, patients must have been compliant with study visits during the Induction Period or the Maintenance Period, respectively. Patients receiving systemic rescue medication (Section 6.3) will be required to washout for 5 half-lives prior to initiating treatment in the Escape Arm. All patients eligible for the Escape Arm will receive blinded loading doses, based on their prior treatment assignment (see Table 3 below), followed by 250 mg lebrikizumab Q2W through Week 52 on study in an open-label fashion. Patients in the Escape Arm must

comply with study visits every 4 weeks. Patients in the Escape Arm, not achieving or maintaining an EASI50 score after 8 weeks of treatment will be terminated from the trial.

Table 3: Escape Arm Dosing Schedule by Treatment Group

Induction Group Assignment	Maintenance Treatment Assignment	Maintenance Loading Dose (Blinded)	Week 20 to 50 (Unblinded: 250mg Q2W)
Patients entering Escape Arm at Week 16			
Active	Escape arm	Week 16: one active and one placebo injection Week 18: one active and one placebo injection	One active injection
Placebo	Escape arm	Week 16: two active injections Week 18: two active injections	One active injection
Patients entering Escape Arm at Week 24, 32, 40 and 48			
	Lebrikizumab 250 mg Q2W	At entry: one active and one placebo injection At next administration: one active and one placebo injection	One active injection
	Lebrikizumab 250 mg Q4W	At entry: one active and one placebo injection At next administration: one active and one placebo injection	One active injection
	Placebo	At entry: two active injections At next administration: two active injections	One active injection

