During the 16-week Induction Period, approximately 400 patients will be stratified and randomized 2:1 to either 250 mg lebrikizumab (loading dose of 500 mg given at Baseline and Week 2) or placebo by subcutaneous (SC) injection every 2 weeks (Q2W). All study drug injections will be administered in the clinic.

After completion of the Week 16 visit, patients who have responded to treatment [defined as having an IGA of 0 or 1 or a 75% reduction in EASI from Baseline to Week 16 (EASI-75)] will enter the Maintenance Period and will be re-randomized 2:2:1 to one of the following treatment groups: lebrikizumab 250 mg Q2W, lebrikizumab 250 mg given every four weeks (Q4W), or placebo Q2W. Patients will be instructed to self-administer study drug at home.

Responders who received placebo during the first 16 weeks of the study and who are re-randomized to lebrikizumab arms will receive a loading dose of lebrikizumab of either 500 mg given at Week 16 or 500 mg given at Weeks 16 and 18, based on the active treatment group assigned in Maintenance.

Patients who do not achieve an IGA of 0 or 1 or an EASI-75 at Week 16, and those patients not maintaining an EASI-50 response following re-randomization at Week 24, 32, 40 or 48, will be assigned to an Escape Arm and receive lebrikizumab 250 mg as long-term treatment Q2W through Week 52. Patients not achieving an EASI-50 response after 8 weeks of treatment in the Escape Arm will be terminated from the study.

Efficacy will be measured through the IGA, EASI, BSA, SCORAD, Pruritus and Sleep-loss scores.

Safety will be assessed by monitoring adverse events, serum chemistry, hematology and urinalysis laboratory testing, physical examination, pulse and blood pressure. An independent Data Safety Monitoring Board will monitor patient safety by conducting formal reviews of

accumulated safety data periodically throughout the trial. Additionally, adolescents will be monitored for hormones.

Serum samples will be collected for pharmacokinetic analysis and immunogenicity.

Quality of life and impact of disease will be assessed using the POEM, DLQI/CDLQI, EQ-5D and PROMIS® Anxiety and Depression measures. Patients reporting comorbid asthma at study entry will complete the ACQ-5.

Photographs of a selected target lesion will be obtained in a subset of patients participating in this study.

Patients completing this 52-week study will be offered the option of continued treatment in a separate long-term extension study (DRM06-AD07).

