8.2.2. Eczema Area and Severity Index (EASI)

The EASI is used to assess the severity and extent of AD; it is a composite index with scores ranging from 0 to 72, with the higher values indicating more severe and/or extensive disease. Assessors must be trained and certified by the Sponsor prior to conducting this assessment.

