Maintenance Secondary Population (MSP)	All patients who were randomized to placebo at Baseline Visit and re-randomized to Lebrikizumab 250 mg Q2W, Lebrikizumab 250 mg Q4W or placebo at Week 16, and received at least one dose of study treatment during the maintenance period .
Modified Maintenance Secondary Population (mMSP)	MSP Population excluding all patients from Site 5042. Patients will be analyzed according to the treatment to which they were re-randomized. Only information prior to escape will be presented. Selective efficacy analyses for the maintenance period will be conducted on the Modified Maintenance Secondary Population.
Maintenance W16 Escape Population	All patients who were NOT re-randomized to Lebrikizumab 250 mg Q2W, Lebrikizumab 250 mg Q4W or placebo but assigned to escape arm at Week 16, and received at least one dose of study treatment during the maintenance period .
Modified Maintenance W16 Escape Population	Maintenance W16 Escape Population excluding all patients from Site 5042. Selective efficacy analyses for the maintenance period will be conducted on the Maintenance W16 Escape Population.
Maintenance W24-48 Escape Population	All patients from Maintenance Primary and Secondary Population who escaped to Lebrikizumab 250 mg Q2W due to EASI-50 non-response at Week 24, 32, 40 or 48.
Modified Maintenance W24-48 Escape Population	Maintenance W24-48 Escape Population excluding all patients from Site 5042. Selective efficacy analyses for the maintenance period will be conducted on the Maintenance W24-48 Escape Population
All Lebrikizumab Safety Population	All randomized patients who received at least 1 dose of lebrikizumab treatment during Combined Induction and Maintenance Periods .

All Lebrikizumab Modified Safety Population	All Lebrikizumab Safety Population excluding all patients from Site 5042. Safety analyses for the Combined Induction and Maintenance Periods will be conducted on All Lebrikizumab Modified Safety Population. Selective safety analyses for the Combined Induction and Maintenance Periods plus the follow-up Period will be conducted on All Lebrikizumab Modified Safety Population.
---	--

Abbreviations: EASI = Eczema Area and Severity Index; IGA = Investigator Global Assessment.

Table KGAC.6.2. Treatment Groups and Comparisons for Each Study Period and Analysis Population

Study Period	Analysis Population	Treatment Groups	Abbreviation	Inferential Comparisons When Applicable

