6.1.3. General Considerations for Analyses During Maintenance Period

Maintenance Period starts at the first injection of study treatment at Week 16 and ends on the date of Week 52 or the ETV (between Weeks 16 and 52) unless specified otherwise.

For the efficacy and health outcome analyses, baseline is defined as the last available value before the first injection in Induction Period and, in most cases, will be the value recorded at Baseline Visit (Day 1).

Unless otherwise specified, efficacy and health outcome scores at Week 16 prior to entering Maintenance Period will be presented for the visit wise reports for Maintenance Period.

Unless specified otherwise, for the safety analyses during Maintenance Period, baseline is defined as the last available value before first injection in Maintenance Period. In most cases, this will be the measure recorded at Week 16. For TEAEs, baseline is the events ongoing just prior to the first injection of the study drug injection at Week 16.

For patients in the Modified Maintenance Primary Population, Modified Maintenance Secondary Population, Maintenance Primary Population, and Maintenance Secondary Population who met escape criteria (EASI-50 nonresponse) and escaped to lebrikizumab 250 mg Q2W at Weeks 24, 32, 40 and 48, only data in the Maintenance Blinded Period (up to the time of escape) will be included in both efficacy and safety analyses.

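### Protocol 5.3.3 glosses loss of response for Maintenance escape with an inverted EASI threshold that describes patients who still have an EASI-50 response

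*Protocol*

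**What the plan says.** Protocol 5.3.3 (Escape Arm) opens escape during Maintenance to patients who "do not maintain an acceptable response during the Maintenance Period (have an EASI score <50% of baseline"). Further on, the same section uses EASI-50 in the opposite and correct direction: Escape Arm patients "not achieving or maintaining an EASI50 score after 8 weeks of treatment will be terminated from the trial".

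Protocol 8.2.2 fixes the direction of the scale, which runs from 0 to 72 "with the higher values indicating more severe and/or extensive disease".

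The other statements of the Maintenance escape rule agree with one another:

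- Protocol synopsis: "those patients not maintaining an EASI-50 response following re-randomization at Week 24, 32, 40 or 48, will be assigned to an Escape Arm".
- Protocol Section 3: the same rule at the same four visits, again as a mandatory assignment.
- SAP Table KGAC.6.1 defines the Week 24-48 escape population as Maintenance patients "who escaped to Lebrikizumab 250 mg Q2W due to EASI-50 non-response at Week 24, 32, 40 or 48".
- SAP 6.1.3 describes patients "who met escape criteria (EASI-50 nonresponse) and escaped to lebrikizumab 250 mg Q2W at Weeks 24, 32, 40 and 48".
- SAP Table KGAC.6.11 codes EASI-50 as a percent change of -50 or lower, and loss of EASI-50 as a percent change above -50.

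**The concern.** The parenthesis gives a numerical cut-off in the section that holds the Escape Arm eligibility, washout and dosing rules, and the cut-off points the wrong way. Applied literally, it would offer escape to patients who are still responding and would not describe those who have relapsed.

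Routing matters for the Week 52 results. Patients who transfer receive lebrikizumab Q2W, open-label after blinded loading doses, and only their data up to escape enter the Maintenance Blinded Period analyses (SAP 6.1.3). Under the maintenance primary estimand (SAP 6.2.2.1 and Table KGAC.6.4), transfer to escape counts as treatment failure and the patient's value is set to baseline. A maintained responder moved in error would therefore be analysed as a failure.

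**Working it through.** The plan gives no figure to reproduce here, so the check is one of logic.

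**Inputs**

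- Scale: EASI 0 to 72, higher is worse (Protocol 8.2.2).
- Minimum baseline: "Eczema Area and Severity Index (EASI) score ≥ 16 at the baseline visit" (Protocol 4.1, criterion 3).
- Percent change = 100 × (score − baseline) / baseline (SAP Table KGAC.6.11).
- EASI-50 kept: percent change ≤ −50, i.e. score ≤ 0.5 × baseline.
- EASI-50 lost: percent change > −50, i.e. score > 0.5 × baseline.
- Parenthesis in 5.3.3: score < 0.5 × baseline.

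**Algebra.** If score < 0.5 × baseline, then percent change < 100 × (0.5 − 1) = −50, so EASI-50 is kept. The parenthesis and loss of EASI-50 cannot both be true of the same patient.

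**Worked values at baseline 16 (cut-off 0.5 × 16 = 8.0)**

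| Score | % of baseline | % change | 5.3.3 parenthesis met? | EASI-50 |
|---|---|---|---|---|
| 12.0 | 75 | −25 | no | lost |
| 8.0 | 50 | −50 | no | kept |
| 7.8 | 48.75 | −51.25 | yes | kept |
| 4.0 | 25 | −75 | yes | kept (EASI-75 also met) |

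The patient at 12.0 has relapsed but is not described by the parenthesis. The patient at 4.0 is an EASI-75 responder and is described by it. The two rules agree only at exactly 8.0, where neither triggers.

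**Whole range.** Baselines 16.0 to 72.0 and scores 0.0 to 72.0 in steps of 0.1 give 561 × 721 = 404,481 pairs. The parenthesis and loss of EASI-50 coincide in 0 pairs and give opposite answers in 404,200. In the remaining 281 the score is exactly half of baseline and neither rule triggers. Read literally, any patient re-randomized on EASI-75 (score at or below 25% of baseline) and still holding that response would qualify for escape.

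**Conditional effect of one misrouted responder.** Take baseline 16 and score 4.0, so percent change is −75. Set to baseline, the analysed change is 100 × (16 − 16)/16 = 0. The shift is 0 − (−75) = 75 percentage points, and the patient turns from EASI-75 responder to non-responder. The EMA Week 52 hierarchy (SAP 6.6.2) has four endpoints (EASI-75, IGA 0/1, Pruritus NRS 4-point reduction, EASI percent change) for each of Q2W and Q4W: 4 × 2 = 8 tests, all handling transfer this way under the maintenance primary estimand.

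**The case against.** The strongest reply is that nobody would be misled. The operative condition is failure to maintain an acceptable response, and the parenthesis only glosses it. For a maintained responder the sentence contradicts itself and does not authorise a transfer. The literal reading would also empty the Maintenance Period of its responders, so a reader would see a slip for less than 50% reduction. The synopsis and Section 3 give the right rule in mandatory terms, with visits, whereas 5.3.3 speaks only of eligibility. Relapsed patients therefore remain covered. The SAP uses the right direction throughout, and its Version 5 rationale treats loss of EASI-50 as what sends patients to escape. The 75-point and 8-test figures show how the estimand treats any transfer; they do not measure an effect of this wording.

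Most of that stands and is why the point is minor. It does not remove the error: recovering the meaning requires replacing a score with a reduction, and the text says score. SAP 6.7 counts patients who enter escape, and SAP 6.16 summarises and lists important protocol deviations. Neither explicitly checks transfers against the EASI values that should have triggered them.

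The LOCF analyses make values after transfer missing and do not count them as failures. That limits the consequence only slightly, because for EASI percent change they are supplementary.

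**Conclusion.** The parenthesis is wrong as written: everyone it describes has an EASI-50 response, and no one it describes has lost it. The error is confined to that parenthesis, and the intended rule can be recovered from its own sentence, a later sentence in the section, the synopsis, Section 3 and the SAP. No planned analysis, population definition or sample size depends on it. No number of affected patients is claimed, and nothing in the documents shows that anyone was misrouted. The 75-point shift is hypothetical: it assumes a site followed the parenthesis over the clause it explains, for a patient at baseline 16 and score 4.0. Severity: minor.

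**What to change.** In Protocol 5.3.3, replace the parenthesis with: *EASI-50 not maintained at Week 24, 32, 40 or 48, i.e. EASI score >50% of baseline (percent change from baseline >−50)*.

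Before the Week 52 lock, list every escape transfer and non-transfer against EASI percent change at those four visits, so that any exception to the intended rule is known before the maintenance analyses. SAP Version 5 was approved before that lock and before maintenance treatment was unblinded, so the listing was still feasible then. By that stage the wording change mainly corrects the record.

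The cost is a one-line clarification and one listing from EASI data already collected. If the clarification is issued as a formal amendment, Protocol 10.1 requires IRB/IEC approval, which across approximately 100 sites is more administrative work than the edit itself suggests.
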